4.5.3 Details on endpoints based on patient-reported outcomes (PROs)

The FACIT-Fatigue, the EQ-5D-5L, the SF-12, the PGIC and PGIS will be utilized in this study. For continuous variables, the overall score and its change from baseline will be analyzed descriptively for each time point.

When applicable missing items will be handled based on the specific patient-reported outcome (PRO) instrument. Subjects missing baseline evaluations would not be included in the PRO analyses.

Functional Assessment of Chronic Illness Therapy (FACIT)-Fatigue Scale

The questionnaires will be analyzed according to the recommendations of the questionnaire authors (see http://www.ser.es/wp-content/uploads/2015/03/FACIT-F_INDICE.pdf). Details of the questionnaire and its algorithm for deriving the score are provided in [Section 5.5.1](#). The questionnaires are considered complete, and the subscale total score can be calculated, if at least 7 of the 13 items were answered by the subject. For each time point, the number and percentage of subjects who complete the questionnaires will be summarized.

The change from baseline in FACIT-F score will be summarized by visit for the FAS.

EQ-5D-5L

The questionnaire will be analyzed based on the EQ-5D-5L scoring manual (see www.euroqol.org). EQ-5D consists of 2 parts – a 5 dimension descriptive system and the EQ visual analogue scale. A copy of the questionnaire is provided in [Section 5.5.2](#).

The descriptive system contains 5 domains: mobility, self-care, usual activities, pain/discomfort and anxiety/depression. The number and percentage of subjects in each response category were tabulated for the FAS. Percentages are based on the number of subjects for whom an assessment is provided at the respective visit.

The EQ visual analogue scale is a visual scale from 0–100 to record a respondent’s overall self-rated health state. The respondent is asked to mark an “X” on the scale then record the corresponding number; 0 refers to the worst possible health state, 100 refers to the best possible health state. This will also be presented alongside the 5 dimension descriptive system scores.

The EQ visual analogue scale will be summarized for the observed response and change from baseline for the FAS.

EQ-5D Index Score

The EQ-5D-5L descriptive system can be converted into a single index value, the EQ-5D index score, by using the “EQ-5D-5L Crosswalk Index Value Calculator” provided by the scoring manual (documents and calculation tools will be downloaded from the EuroQol website). The index scores, derived as country specific, are a major feature of the EQ-5D instrument, facilitating the calculation of quality-adjusted life years (QALYs) that are used to inform economic evaluations of health care interventions.

The derived EQ-5D index scores and change from baseline will be summarized by visit for the FAS.

Additionally, the EQ-5D index score, will be summarized using an ANCOVA (Analysis of Covariance) model, where treatment arm is the fixed effect, and the baseline score is the covariate; a 95% confidence interval for the treatment effect difference and the corresponding p-value will be generated. The treatment difference and 95% CI will be estimated by ANOVA with treatment and baseline value as independent variables.

12-Item Short Form Survey (SF-12)

The questionnaire will be analyzed according to the recommendations of the authors (see <http://campaign.optum.com/optum-outcomes/what-we-do/health-surveys/sf-12v2-health-survey.html>). The SF-12 v2 is a 12-item measure, derived from the original 36-item SF-36, which includes eight (8) health domains which are used to generate a physical component score as well as a mental component score. Each score ranges from 0–100 on a normative scale and may be used to derive a health utility index (SF-6D). A copy of the questionnaire is provided in [Section 5.5.3](#).

The derived scores and change from baseline for the eight health domains, the physical component score, and the mental component score, will be summarized by visit for the FAS.

Additionally, the SF-12 component scores (physical component score and mental component score), will be summarized using an ANCOVA (Analysis of Covariance) model, where treatment arm is the fixed effect, and the baseline score is the covariate; a 95% confidence interval for the treatment effect difference and the corresponding p-value will be generated. The treatment

difference and 95% CI will be estimated by ANOVA with treatment and baseline value as independent variables.

Patient Global Impression of Change (PGIC)

The questionnaire (listed in [Section 5.5.4](#)) will be summarized as an ordinal variable by visit for FAS at the end of the study only.

Patient's Global Impression Of [Fatigue] Severity (PGIS)

The change from baseline in questionnaire (listed in [Section 5.5.5](#)) will be summarized as an ordinal variable by visit for FAS.

Healthcare Resource Utilization

The number of healthcare visits by type (office visit, hospital ER visit, hospitalization, and ICU stay) will be collected and presented in a listing.

4.6 MULTIPLICITY ISSUES

Primary Endpoint

The study primary objective is to compare the treatment effect of BIV009 with placebo in responder rate (responder definition in [Section 7.2](#)).

The study is designed to test the primary hypothesis whether patients treated with BIVV009 will achieve a response rate greater than those treated with Placebo. The primary statistical hypothesis is written as:

H0: response rate (BIVV009) \leq response rate (Placebo)

H1: response rate (BIVV009) $>$ response rate (Placebo),

where the response rate of a treatment group is the proportion of patients in the intent-to-treat (ITT) population who meet the response criteria defined in of the protocol. This will be tested using a 1-sided test at the 0.025 significance level.

Key Secondary Endpoints

Secondary hypotheses, corresponding to the treatment difference for the key secondary endpoints, will be tested only if the primary null hypothesis is rejected at a 1-sided significance level of 0.025.

The key secondary endpoints will be tested using a sequential closed procedure with alpha of 0.05 for each test in the order indicated below:

1. Mean change from baseline in Hgb at the treatment assessment timepoint in BIVV009 arm vs in placebo arm

2. Mean change from baseline in FACIT-F Score at treatment assessment timepoint in BIVV009 arm vs in placebo arm

The following secondary endpoints will be analyzed descriptively:

- Mean change from baseline in bilirubin at the treatment assessment timepoint in BIVV009 arm vs in placebo arm
- Mean change from baseline in Lactate Dehydrogenase (LDH) at the treatment assessment timepoint
- Incidence of Solicited Symptomatic Anemia

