### 7.3.2 Methods of analysis

Each patient in the FAS will be classified as a responder or non-responder per the response criteria, and will be compared between treatment groups using Cochran-Mantel-Haenszel test at the significance level of 0.05. The difference in the proportion of responders between groups will be calculated with a 95% exact confidence interval (CI). To assess the hematology component of response, the mean of the non-missing Hgb assessments at the Week 23, Week 25, and Week 26 analysis visits (treatment assessment endpoint) will be used. Visit windows will be used to assign analysis visits, as detailed in the SAP. Patients missing all three analysis visits will be counted as non-responders. Sensitivity analyses will be performed to evaluate the impact by the missing data, when appropriate. Details will be specified in the SAP.

Secondary endpoints, defined as follows, will be tested only when the primary endpoint is statistically significant:

1. Mean change from baseline in Hgb at the treatment assessment endpoint (mean of values at Week 23, 25, and 26)
2. Mean change from baseline in bilirubin (excluding patients with Gilbert's Syndrome) at the treatment assessment endpoint
3. Mean change from baseline in QOL, as assessed by the change in FACIT-fatigue scale scores at the treatment assessment endpoint
4. Mean change from baseline in LDH at the treatment assessment endpoint
5. Incidence of solicited symptomatic anemia at EOT

The change from baseline variables will be analyzed using analysis of covariance (ANCOVA) with baseline as covariate. A multiple testing procedure will be specified in the SAP to control the overall Type I error rate among the secondary endpoints.

As a sensitivity analysis, the efficacy analysis will be repeated with patients stratified by previous rituximab therapy and/or cytotoxic therapy versus patients who are naïve to rituximab therapy and/or cytotoxic therapy using the FAS.

Other efficacy assessments will be summarized by overall population using descriptive statistics, proportions and graphically where applicable.

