4.4.2 Supportive secondary endpoint(s)

Additional analyses for hemoglobin and bilirubin

To further understand the clinical effect of BIVV009 in increasing hemoglobin level compared with placebo, the number of subjects with an increase of hemoglobin level from baseline ≥ 1 g/dL, ≥ 1.5 g/dL, ≥ 2 g/dL and ≥ 3 g/dL at TAT will be reported for BIVV009 and for placebo.

Mean Change from Baseline in Bilirubin by visit (including TAT)

Total bilirubin will be summarized by-visit, including change from baseline, using the Full Analysis Set, with subjects with Gilbert's syndrome or unknown Gilbert's test result excluded.

If the number of subjects with unknown Gilbert's syndrome status is greater than 2, additional sensitivity analysis will be performed to include such subjects (unknown Gilbert's syndrome).

Mean Change from Baseline in Lactate Dehydrogenase (LDH) by visit (including TAT)

LDH will be summarized by-visit, including change from baseline, using the Full Analysis Set.

Additional descriptive analyses will be performed for LDH isoforms.

Incidence of Solicited Symptomatic Anemia

- Incidence of solicited symptomatic anemia will be summarized by visit descriptively using the FAS. The summaries will be based on observed data only and missing grades will not be imputed.

- An improvement in each anemia symptom is defined as at least 1 grade reduction from baseline; whereas worsening is defined as at least 1 grade increase from baseline. The percentage of improved and worsened subjects for each symptom will be presented by visit; this percentage is calculated based on the number of subjects with no missing grade at both baseline and each post-baseline visit.
- The improvement (worsening) in all anemia symptoms is defined as at least 1 grade reduction (increase) in at least 1 symptom, and no worsening (improvement) in other remaining symptoms. The proportion of subjects improved and worsened in all anemia symptoms will be summarized by visit.

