4.5.2 Main analytical approach

Continuous Endpoints

The continuous endpoints will be summarized by visit and treatment arm using descriptive statistics for the FAS according to [Section 4.1](#).

For EQ-5D index score and SF-12 component scores (physical component score and mental component score), an ANCOVA (Analysis of Covariance) model will be implemented, where treatment arm is the fixed effect, and the baseline score is the covariate; a 95% confidence interval for the treatment effect difference and the corresponding p-value will be generated. The treatment difference and 95% CI will be estimated by ANOVA with treatment and baseline value as independent variables.

Response (Categorical) Endpoints

The categorical endpoints will be summarized descriptively by visit for the FAS according to [Section 4.1](#) with the exception of total healthcare resource utilization at EOT (Part A), which will be presented in a listing.

All thromboembolic events reported (in Adverse Events) will be reviewed and determined by internal medical staff along with investigators. In case that there are discrepancies between the medical review and investigators' assessment, separate analyses will be carried out for both sets of events. Date of event occurrences will be verified. The detailed listing for all events will be provided including date (study day) of onset, verbatim terms of the event, and the flag for whether the event occurred after the first 5 weeks of study drug administration. Incidence of thromboembolic events will be calculated as the total number of thromboembolic events after the first 5 weeks of study drug administration divided by the total subject-years of time for observation (ie, time from Week 5 through Week 26 or EOT visit for subjects who discontinue early). All events from Week 5 through Week 26 or EOT visit for subjects who discontinue early will be included. A 95% exact CI will be provided.

Time-to-Event Endpoints

All time-to-event endpoints will be analyzed by treatment group for the FAS using the Kaplan-Meier method outlined in [Section 4.1](#). For subjects who receive transfusions after Week 5 infusion, the time to normalization will be censored at the study day of the transfusion visit. For subjects who do not experience normalization, the data will be censored at the study day of the last assessment in Part A.

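### The Part A SAP replaces the protocol's baseline-adjusted comparison of bilirubin and LDH with descriptive summaries, so no adjusted treatment difference or CI is planned for either secondary haemolysis endpoint.

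*SAP*

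**What the plan says.** Protocol 7.3.2 lists five secondary endpoints to be tested if the primary succeeds. Item 2 is "Mean change from baseline in bilirubin (excluding patients with Gilbert's Syndrome) at the treatment assessment endpoint" and item 4 is "Mean change from baseline in LDH at the treatment assessment endpoint". For this kind of endpoint it states: "The change from baseline variables will be analyzed using analysis of covariance (ANCOVA) with baseline as covariate". On multiplicity it adds: "A multiple testing procedure will be specified in the SAP to control the overall Type I error rate among the secondary endpoints". The synopsis repeats this plan.

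The Part A SAP narrows it. Section 4.4.1 keeps Hgb and FACIT-F as key secondary endpoints, each with a baseline-adjusted MMRM, a between-arm difference and a 95% CI. Section 4.6 places bilirubin, LDH and symptomatic anemia under "The following secondary endpoints will be analyzed descriptively". Section 4.4.2 then says "Total bilirubin will be summarized by-visit, including change from baseline, using the Full Analysis Set" (without patients who have Gilbert's syndrome or an unknown test result) and "LDH will be summarized by-visit, including change from baseline, using the Full Analysis Set". Its headings add TAT to the visits. SAP 4.1 defines a continuous summary as n, mean, SD, median, minimum and maximum.

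Protocol section 7 gives the SAP precedence where the two differ.

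**The concern.** Bilirubin and LDH measure haemolysis directly, and the secondary efficacy objective concerns laboratory parameters of hemolysis and anemia. Under the SAP, the study report would give arm-level means for these two markers but no planned estimate of the treatment effect and no interval around it.

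The choice does not look deliberate:

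- **Inverted ranking.** The SAP 4.5.2 sentence that begins "For EQ-5D index score and SF-12 component scores (physical component score and mental component score), an ANCOVA" goes on to require a treatment difference, 95% CI and p-value for exploratory scores. Those scores are also outside the hierarchy, so saving alpha cannot explain why the secondary markers get less.
- **Internal mismatch.** SAP 1.2.1 says a hypothetical estimand will serve the laboratory-defined secondary endpoints. Table 3 applies it only to Hgb and FACIT-F, and Table 9 only to Hgb. Nothing says how bilirubin or LDH values after transfusion or prohibited medication are handled.
- **No stated reason.** The SAP version history says nothing major changed, its change table records only the switch to CMH, and Appendix 2 lists no change. Protocol Version 8 (04 November 2020) postdates SAP Version 2 (02 October 2020) and amended 7.3.2 to bring in CMH, yet kept the ANCOVA sentence and the five-endpoint list.

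**Working it through.** **Step 1: does any other SAP text restore a model for bilirubin or LDH?**

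| SAP location | What it offers | Covers bilirubin or LDH? |
|---|---|---|
| 1.2.1, text | Hypothetical estimand for laboratory-defined secondary endpoints | In words only; no model |
| Table 3 | Hypothetical, modified and de-facto estimands | Hgb and FACIT-F only |
| 4.4.1.2 and Table 9 | MMRM with contrast over Weeks 23, 25 and 26 | Under the Hgb heading; only FACIT-F is told to reuse it |
| 4.4.2 | Summaries by visit and TAT | Yes, no between-arm effect |
| 4.5.1 and 4.5.2 | Proportions normalizing; Kaplan-Meier times to normalization | Yes, by arm, no between-arm effect or CI |
| 4.6 | Names the arms being compared for bilirubin | Under the descriptive line |

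No section gives an adjusted difference or CI for either marker.

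**Step 2: the plan's own figures.** The documents give no SD, correlation or power for bilirubin or LDH, so there is no stated figure to reproduce on this point. The only power figure is 87% for the responder endpoint (20 per arm, 85% against 35%, two-sided 5%). Exact enumeration with Fisher's test gives 87.5%. This point does not affect it.

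**Step 3: precision lost by not adjusting.** Assume equal variance s² at baseline and follow-up, with correlation r between them (r is not in the documents).

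- Per-patient variance of a raw change score: 2s²(1 − r)
- Residual variance under ANCOVA: s²(1 − r²)
- Ratio: (1 − r²) / [2(1 − r)] = (1 + r)/2
- CI width ratio: √[(1 + r)/2], ignoring one degree of freedom

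| r (assumed) | 2(1 − r) | 1 − r² | Variance ratio | CI width ratio | CI narrower by |
|---|---|---|---|---|---|
| 0.3 | 1.40 | 0.91 | 0.65 | 0.806 | 19% |
| 0.5 | 1.00 | 0.75 | 0.75 | 0.866 | 13% |
| 0.7 | 0.60 | 0.51 | 0.85 | 0.922 | 8% |

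**Step 4: what the adjusted CI would look like.** Half-width in SD units = t(0.975, 2n − 3) × √(2/n) × √(1 − r²). For n = 20 per arm and r = 0.3: 2.026 × 0.316 × 0.954 = 0.611.

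| r (assumed) | n = 20 per arm | n = 16 per arm (assumed, for Gilbert's exclusions or missing data) |
|---|---|---|
| 0.3 | 0.611 | 0.690 |
| 0.5 | 0.555 | 0.626 |
| 0.7 | 0.458 | 0.516 |

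The adjusted interval would thus be roughly ±0.5 to ±0.7 SD.

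**The case against.** The strongest reply is that this is a permitted narrowing with little practical loss. Several parts of it stand.

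- The protocol leaves the multiple testing procedure to the SAP, and the SAP prevails. With about 40 patients, confining formal tests to Hgb and FACIT-F is a legitimate choice.
- The summaries include change from baseline and TAT. A reader might infer that the trial could not say how bilirubin or LDH moved against placebo. The documents do not support that: n, mean and SD by arm yield an unadjusted difference and a two-sample 95% CI, unbiased under randomization. Nor do the summaries ignore baseline, which is subtracted, though not adjusted for by regression.
- By-arm normalization proportions, the proportion with LDH at or below 1.5 × ULN, and times to normalization are also planned. Hgb, under the same secondary objective, does have a modelled difference with CI.
- Symptomatic anemia sits in the same descriptive list, so a reader might infer that it lost an adjusted analysis too. It did not: the ANCOVA sentence covers change-from-baseline variables only, and the protocol names no method for that endpoint.
- Appendix 2 describes itself as summarizing changes in protocol amendments, and SAP 4.6 states the descriptive status openly. The fault is a missing reason, not concealment.

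None of this explains dropping the adjusted estimate itself. An endpoint can leave the hierarchy and still have a difference and CI reported, as the SAP does for EQ-5D and SF-12.

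**Conclusion.** The point holds for bilirubin and LDH. The protocol's planned baseline-adjusted comparison at the treatment assessment endpoint is absent from the governing SAP, no reason is recorded, and the estimand that SAP 1.2.1 promises is not carried through to these endpoints.

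The size is modest. The loss is a prespecified, reported, adjusted estimate plus some precision: CIs about 19%, 13% or 8% wide of what they could be, taken as the narrowing that adjustment would bring at r = 0.3, 0.5 and 0.7. Those percentages rest on assumed correlations and equal variances. They compare two estimators, whereas the SAP plans neither. The textual finding needs no assumption.

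It does not affect the primary conclusion or type I error, and the documents do not support a demand to return either endpoint to formal testing. It should be fixed, but it does not threaten the trial's main result.

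**What to change.** In SAP 4.4.2, for bilirubin (keeping the planned Gilbert's exclusion) and LDH at TAT:

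1. Report the baseline-adjusted BIVV009-placebo difference with 95% CI, from the protocol's ANCOVA or the MMRM contrast over Weeks 23, 25 and 26 already used for Hgb. Name one of the two in advance.
2. Treat values after transfusion or prohibited medication as missing, as in the Hgb hypothetical estimand, and add both endpoints to Table 3 so that it agrees with SAP 1.2.1. Under ANCOVA a patient whose TAT values are all set to missing drops out; the MMRM still uses that patient's earlier visits.
3. Label the result as outside the alpha-controlled hierarchy. A nominal p-value is not needed.
4. Record in Appendix 2 that these endpoints left the protocol's testing plan, and why.

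If the MMRM is chosen, correct the pseudo-code before reuse: treatment is missing from the CLASS statement although the ESTIMATE line assigns it two coefficients.

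The cost is two extra model outputs. No new data are needed, because the chemistry panel is scheduled at every Part A dosing visit and at Day 182, and no alpha is spent. A difference in proportions with CI for symptomatic anemia at EOT would be a useful optional addition, separate from the dropped ANCOVA.

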4.7 SAFETY ANALYSES

All safety analyses will be performed on the Safety Analysis Set as defined in [Section 3](#), stratified by treatment arm, unless otherwise specified, using the following common rules:

- The analysis of the safety variables will be essentially descriptive, and no testing is planned.
- Safety data in participants who do not belong to the safety population (eg, exposed but not randomized) will be provided.

4.7.1 Extent of exposure

The extent of IMP exposure will be assessed by the duration of IMP exposure and treatment compliance and summarized for the Safety Analysis Set. Per the protocol, all subjects rolling over to Part B are to receive a loading dose (in a blinded manner). For analysis of Part A exposure, this loading dose will not be included in the Part A database. Thus, Part A exposure will end 1 minute prior to the date/time of the Week 26 loading dose, and Part B exposure will start on the date/time of the Week 26 loading dose.

Duration of IMP exposure

Study drug exposure, measured by the duration of study treatment, number of administrations, and total actual BIVV009 dose will be summarized for the Safety Analysis Set.

The duration of the study treatment (in weeks) in Part A is defined as:

- $(\text{Date of Week 26 visit} - \text{Date of first dose} + 1)/7$, if a subject enrolls into Part B;
- $(\text{Date of last dose} - \text{Date of first dose} + 15)/7$, if a subject discontinues study treatment early in Part A or does not enroll into Part B.

Treatment compliance

Study drug compliance for a subject is measured by the percent of number of doses received out of the number of protocol-specified doses. For example, for a subject who completes Part A treatment, the number of protocol-specified doses is 14. The compliance of the subject will be the

number of doses received divided by 14 expressed in percentage. For a subject who discontinues early in Part A, the number of protocol specified doses is the number of scheduled doses prior to the date of discontinuation. The proportion of subjects whose compliance is less than 80%, 80% – <100%, and $\geq 100\%$ will also be summarized. In addition, the number of subjects and number of doses administered out of study windows and number of partial infusion doses will also be summarized.

